#### 4. After Discharge:

- Patients will record the following information after discharge up until 96 hours from their surgery:
  - VAS scores every 6 hours
  - Pain medication consumption (dosages, times)
  - Opioid-related side effects
  - Level of satisfaction with pain management
- Study staff may conduct reminder phone calls to ensure patients complete outpatient data collection. The outcome assessor will be blinded to the treatment group.
- Patients will record their VAS pain scores again at their 1st postop appointment, which typically occurs 10-18 days after surgery.

Sample Size: There will be 60 patients in each group, for a total study population of n = 120.

Study Locations: This will be a multi-center study. The sample size will enroll 120 (to account for 15% drop out rate) patients total, with approximately 30 patients enrolled at each site. The other participating sites are as follows:

[name]  
Sports Medicine and Shoulder Service  
University of Texas, Southwestern Medical Center  
[name]  
[name]

[name]  
MedStar St. Mary's Hospital  
[name]  
[name]

[name]  
William Beaumont Army Medical Center  
[name]  
[name]

**Aim #2:** Determine the length of stay of liposomal bupivacaine compared to interscalene nerve block in patients undergoing total shoulder arthroplasty and calculate costs associated with any differentials.

- b. Study duration and number of study visits required of research participants.

Patients will be enrolled in this study for 2 weeks after their surgical date. This time frame will include their hospital stay and include their time at home after discharge up until 96 hours after their surgery, and their 2-week postop appointment data. If patients are not scheduled for their postop appointment within 10-18 days after surgery (which is standard clinical practice), the study team will call the patient to obtain their pain score and medication data. Patient names will be stored in a password-protected database for 30 days after discharge to calculate 30-day readmission rates.

Routine patient follow up is typically at 3, 6, and 12 months for the first year. Pain data and patient reported outcomes are collected at these visits as routine clinical care. Patients routinely complete the ASES and EQ-5D questionnaires at their 12 month follow up appointment.

- c. Blinding, including justification for blinding or not blinding the trial, if applicable.

Patients will be masked by performing the ISNB under sedation. They will not be completely blinded to their treatment group due to the fact that the Exparel group will not get a needle puncture at the site of the typical ISNB location in the neck since Exparel is injected intraoperatively in the surgical field while the patient is completely under general anesthesia. While the patient and surgeon cannot be blinded for this study, the outcome assessor will be masked to prevent bias in the data collection process.

- d. Justification of why participants will not receive routine care or will have current therapy stopped.

N/A

- e. Justification for inclusion of a placebo or non-treatment group.

N/A

- f. Definition of treatment failure or participant removal criteria.

Treatment is a one-time intervention for the nerve block. The assessment of their VAS pain score is routine clinical practice.

- g. Description of what happens to participants receiving therapy when study ends or if a participant's participation in the study ends prematurely.

In these cases, routine clinical care will continue based on the patient's needs.

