**2. Objectives (include all primary and secondary objectives)**

**Aim #1:** Determine clinical outcomes as they relate to pain control of the interscalene nerve block vs. liposomal bupivacaine injection in patients undergoing total shoulder arthroplasty.

This will be evaluated using the Visual Analog Scale (VAS) pain score and pain medication data and side effects from opioids (nausea/vomiting, GI distress, itching, etc) from inpatient medical records and through daily follow-up questionnaires after patients are discharged until 96 hours after surgery. Data will be collected at routine clinical follow up appointments after surgery.

**Aim #2:** Determine the length of stay of liposomal bupivacaine compared to interscalene nerve block in patients undergoing total shoulder arthroplasty and calculate costs associated with any differentials.

**3. Background** (briefly describe pre-clinical and clinical data, current experience with procedures, drug or device, and any other relevant information to justify the research)

We conducted a retrospective cohort analysis of 58 shoulder arthroplasties performed by a single surgeon. Patients who underwent total, reverse, and hemiarthroplasties were included. The control group included patients who received interscalene nerve blocks for postoperative pain control. The experimental group included patients who received periarticular liposomal bupivacaine injections. Baseline demographic data included age, sex, body mass index (BMI), and American Society of Anesthesiologists' (ASA) classification of physical health. We measured length of stay (LOS), pain medication administration, numeric rating scale (NRS) pain scores at four time intervals postoperatively (0.5 hours, 8-14 hours, 18-24 hours, 27-36 hours). Statistical analysis was performed.

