There were 21 patients in the IS nerve block group and 37 patients in the liposomal bupivacaine group who met all inclusion criteria. Baseline demographic data for age ( $p=0.53$ ), sex ( $p=0.71$ ), BMI ( $p=0.09$ ), and ASA ( $p=0.33$ ) did not differ between groups. The primary outcome measure, NRS pain score, showed no significant differences between groups at 0–1 hours after surgery ( $P = .99$ ) or 8–14 hours after surgery ( $P = .208$ ). At 18–24 hours after surgery, the liposomal bupivacaine group had a lower mean NRS score than the ISNB group ( $P = .001$ ). This was statistically significant when taking repeated measures of variance into account (Fig. 1). Mean NRS score was also lower for the liposomal bupivacaine group at 27–36 hours after surgery ( $P = .029$ ). This was not statistically significant when repeated measures of variance were considered (Table II).

There was no difference in the amount of intravenous acetaminophen given during the hospital stay between groups. There was no statistically significant difference in opioid consumption on postoperative day 1 in the hospital ( $P = .59$ ). However, there were significant differences between groups on postoperative days 2 and 3 (Fig. 2). On postoperative day 2, the ISNB group required significantly more opioids (112 mg) than the liposomal bupivacaine group (37 mg) ( $P = .001$ ). The ISNB group also required significantly more opioids (25 mg) on postoperative day 3 than the liposomal bupivacaine group (5 mg) ( $P = .002$ ).

Sixteen of 37 patients in the liposomal bupivacaine group and 2 of 21 in the ISNB group (Table III) were discharged on the day after surgery. The mean LOS was  $46 \pm 20$  hours for the liposomal bupivacaine group and  $57 \text{ hours} \pm 14$  hours for the ISNB group ( $P = .012$ ).

There were no major cardiac or respiratory events in either group. No long-term paresthesias or neuropathies were noted. There were no readmissions for either group.

Liposomal bupivacaine injections may provide better pain control 18-24 hours after surgery and shorten hospital stays after shoulder arthroplasty compared to interscalene nerve blocks as a means of postoperative pain control. Based on these results, larger analytic studies including randomized trials should be performed to explore the potential benefits of liposomal bupivacaine injections for pain control after shoulder arthroplasty.

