#### **4. Study Procedures**

- a. Study design, including the sequence and timing of study procedures (distinguish research procedures from those that are part of routine care).

Study Design: After the decision to proceed with shoulder replacement surgery, patients will be asked to participate in this prospective randomized clinical trial.

Study Groups:

- Group 1 will receive interscalene nerve block.
- Group 2 will receive liposomal bupivacaine with local bupivacaine for postoperative analgesia.

Study Procedures:

1. Before Surgery: The Informed Consent process will be completed prior to any data collection. Consent will be completed after explanation of each treatment group and the data to be collected. The following baseline data will be collection prior to surgery:

- Demographics (including age, sex, BMI, work status, living environment)
- Medical and Surgical History
- ASA Physical Status Classification
- Charlson Comorbidity Index Score
- Pain History and Medications
- VAS pain score

2. Randomization: Subjects will be randomized prior to surgery into one of the two perioperative analgesia groups. Randomization will be stratified by gender.

3. Surgery/Inpatient Stay:

- Group 1: Patients in the interscalene nerve block group will be given a single shot block in the preoperative area by a fellowship-trained anesthesiologist. The shot will contain a local anesthetic like 5% Ropivacaine (5 mg/1 mL) with a 44 millimeter 22 gauge needle with the patient in the supine position.
- Group 2: The surgeon at each site will be trained prior to enrollment on the correct way to perform Exparel injections intraoperatively. The surgeon will give patients in the liposomal bupivacaine group the periarticular injection

containing 266 mg of the drug in 40 mL injectable saline in the operating room; local 0.5% bupivacaine-epinephrine will also be used not to exceed dose limits.

- Surgical/Inpatient Data Collection:
  - Pre-op procedure time
  - Surgical time
  - PACU time
  - Admission/Discharge time and date
  - Estimated blood loss
  - Procedures performed
  - Inpatient pain medications administered
  - Patient VAS scores every 6 hours after surgery

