## 7. Study Statistics

- a. Primary outcome variable.

- VAS pain score at 24 hours postop.

- b. Secondary outcome variables.

- VAS scores at all other data points,

- Pain medication consumption (narcotics, NSAIDs, Tylenol)
- Opioid-induced side effects (nausea, vomiting, constipation)
- Length of hospital stay
- 30 day readmission rate.

- c. Statistical plan including sample size justification and interim data analysis.

A power analysis was performed to determine the sample size needed to determine noninferiority between groups with respect to VAS pain score. The minimal clinically important difference of VAS is 1.4 cm^13. The number was found to be 42 patients in each group, for a total n = 84. To ensure we reach this number, each of the 4 sites will aim to enroll 30 patients, to account for drop out.

The age of the two treatment groups will be compared using t-test. Sex distribution and the ASA scores of the groups will be compared using a chi-squared test and a Fisher exact test, respectively.

The median and interquartile range of the VAS scores at each of the time points measured will be tabulated by treatment group, and at each time point the difference between groups will be tested using non-parametric rank sum tests.

We will test the longitudinal trajectory of VAS scores over time, taking into account repeated measurements in the same patients using linear mixed model analysis. Treatment group, time period as a categorical variable, and the interaction between treatment and time period will be included as fixed effects, and patient ID will be included as the random effect. An initial omnibus test will be performed for all treatment and treatment by time interaction effects. If significant, the treatment by time interaction will be tested subsequently for each of the measurement periods.

The association of day of discharge (as a categorical variable) with treatment will be tested using the Fisher exact test.

- d. Early stopping rules.

We will monitor operative and post-operative complications including implant failures, nerve injuries, hematomas, and infections. We do not anticipate issues with these complications, as both techniques are in routine use in our current clinical practice. We did not find any differences in the complication rates in our retrospective cohort analysis.

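### Opioid side effects switch from chart review to patient report at discharge, so ascertainment could differ modestly by arm if length of stay differs

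*Combined protocol and SAP*

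**What the plan says.** - **Source of side effects.** Section 2, Aim 1, obtains "side effects from opioids (nausea/vomiting, GI distress, itching, etc) from inpatient medical records and through daily follow-up questionnaires after patients are discharged", up to 96 h after surgery.
- **Inpatient list.** Section 4a (Surgery/Inpatient Stay) includes "Inpatient pain medications administered" and "Patient VAS scores every 6 hours after surgery". It has no item for side effects or satisfaction.
- **Post-discharge list.** Section 4a (After Discharge) states: "Patients will record the following information after discharge up until 96 hours from their surgery". The items are six-hourly VAS, medication taken, opioid side effects and "Level of satisfaction with pain management".
- **Outcomes.** Section 7b includes "Opioid-induced side effects (nausea, vomiting, constipation") and length of stay among the secondary outcomes. Satisfaction is not listed there.
- **Analysis.** Section 7c gives no analysis for side effects or satisfaction and does not mention the change of source at discharge.
- **Prior data.** In the Section 3 cohort, "Sixteen of 37 patients in the liposomal bupivacaine group and 2 of 21 in the ISNB group" went home the day after surgery. Mean stay was 46 h (SD 20) against 57 h (SD 14).

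**The concern.** One secondary outcome is measured by two methods, and each patient changes method on leaving hospital. A chart entry depends on what staff noticed and wrote down, whereas a questionnaire asks the patient. If the two do not detect nausea, itching or constipation equally well, the recorded rate depends on how long the patient stayed.

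Stay is determined after randomisation and may be shortened by one of the treatments; Aim 2 exists to find out. Randomisation cannot balance a switch point that treatment moves, and masking the outcome assessor does not make the sources equal. The arm that goes home earlier would be asked directly for longer and would appear to have more side effects.

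That runs against a benefit the sponsor has reason to look for. In the Section 3 cohort the block group used more opioid on day 2 (112 against 37 mg) and day 3 (25 against 5 mg).

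Satisfaction has a different gap: nothing is recorded before discharge. A patient in hospital for the full 96 h would have no rating and would never be asked directly about side effects.

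**Working it through.** **1. The cohort's own figure.** Section 3 gives P = .012 for 46 h (SD 20, n = 37) against 57 h (SD 14, n = 21) and names no test. From these summaries a Welch t-test gives P = 0.018 and a pooled t-test P = 0.030. Allowing for rounding of the printed values, Welch spans 0.008 to 0.035 and pooled 0.016 to 0.053. The stated value is compatible with Welch but cannot be confirmed.

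**2. Size of the difference in stay.**
- Difference in means: 57 − 46 = 11 h. SE = √(20²/37 + 14²/21) = 4.5 h; Welch 95% CI 2 to 20 h.
- Home the day after surgery: 16/37 = 43.2% and 2/21 = 9.5%. Difference 33.7 points (Wald 95% CI 13 to 54); Fisher exact P = 0.0085.

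**3. Time under direct questioning.** Treating stay as counted from surgery (an assumption), the time is 96 − mean stay:
- liposomal bupivacaine: 96 − 46 = 50 h (52% of 96 h)
- block: 96 − 57 = 39 h (41%)
- ratio: 50/39 = 1.28

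**4. Effect on the recorded rate.** The documents give no capture rates. Assume equal true rates in both arms, constant over 96 h, 90% capture by questionnaire and chart capture c. Then recorded share = [stay × c + (96 − stay) × 0.9] / 96.

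| c | Liposomal bupivacaine | Block | Ratio |
|---|---|---|---|
| 0.3 | 58.8/96 = 0.612 | 52.2/96 = 0.544 | 1.13 |
| 0.5 | 68.0/96 = 0.708 | 63.6/96 = 0.663 | 1.07 |
| 0.7 | 77.2/96 = 0.804 | 75.0/96 = 0.781 | 1.03 |
| 0.9 | 0.900 | 0.900 | 1.00 |

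**5. When the events occur.** Let stays follow normal distributions with the cohort means and SDs, truncated to 12–96 h. Let f be the share of the event window spent in hospital. The recorded share is f × c + (1 − f) × 0.9.

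| Events spread over | f, liposomal bupivacaine | f, block | Ratio, c = 0.3 to 0.7 |
|---|---|---|---|
| 0–96 h | 0.496 | 0.593 | 1.11 to 1.02 |
| 24–72 h | 0.486 | 0.667 | 1.22 to 1.05 |
| 0–24 h | 0.979 | 0.999 | 1.04 to 1.005 |

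For example, at 24–72 h with c = 0.3: (0.486 × 0.3 + 0.514 × 0.9) / (0.667 × 0.3 + 0.333 × 0.9) = 0.608/0.500 = 1.22. If out-of-range stays are set to the limits rather than excluded, the last two rows become 1.24 to 1.05 and 1.08 to 1.01, and the ordering is unchanged.

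**6. On the risk scale.** Assume the same true 96 h risk p in both arms, full capture by questionnaire, chart sensitivity s, and stays as above with out-of-range values set to the limits. Recorded risk is the mean over patients of 1 − exp{−h[s × stay + (96 − stay)]}, with h = −ln(1 − p)/96. The spurious excess with liposomal bupivacaine, in percentage points, is:

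| True risk | s = 0.3 | 0.5 | 0.7 | 0.9 | 1.0 |
|---|---|---|---|---|---|
| 30% | 2.2 | 1.5 | 0.9 | 0.3 | 0 |
| 50% | 3.4 | 2.3 | 1.3 | 0.4 | 0 |

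An event rate that halves every 24 h gives nearly the same values.

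**The case against.** The collection rule is identical in both arms. An imbalance arises only if stay differs in the trial, and the evidence for that is a retrospective, non-randomised, single-surgeon cohort of 58, projected to four sites. The documents do not say how ward staff elicit side effects, so under-recording in the chart is an assumption; with equal capture the bias is zero. Even under the assumed values the excess is small beside sampling error. With 60 per arm and 30% risk, the standard error of a difference is √(2 × 0.3 × 0.7/60) = 8.4 points. All of this stands, and it limits the size of the point and the confidence in it. It does not remove the defect, because the change of source at discharge is in the text and this bias does not shrink as patients are added.

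A reader might infer more than the documents support:

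- *All secondary outcomes are affected.* VAS is six-hourly in both settings, and length of stay and readmission do not use the patient record. Medication use does change source, from drugs administered to drugs self-recorded, but it was not quantified here.
- *Satisfaction is taken from the chart in hospital.* It has no inpatient source and is not a listed secondary outcome. Patients discharged before 96 h share the same end of window, so late ratings could be common to both arms.
- *The in-hospital VAS method needs changing too.* No change of VAS method at discharge is shown, so nothing is proposed for it.

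**Conclusion.** The point holds in a limited form, with moderate confidence. For opioid side effects the source changes at discharge, discharge is a post-randomisation event that treatment may influence, and the plan neither prevents nor handles this. If the cohort's difference in stay recurs and charts record less than direct questioning, the arm discharged earlier would show a spurious excess. The rate ratio is about 1.03 to 1.13 under the assumed capture rates, smaller if events fall in the first 24 h and larger if they fall at 24–72 h. It is 1 if stay or capture is equal.

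It is tempting to conclude that the bias could reverse a true reduction. A bias of this size could reverse only a reduction of about the same size; the supportable statement is that it could partly mask one. The primary outcome, VAS at 24 h, is not affected. For satisfaction, the finding is that nothing is collected before discharge.

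**What to change.** In Sections 2 and 4a, give every patient the existing side-effect and satisfaction questionnaire on one fixed schedule counted from surgery (24, 48, 72 and 96 h), whether in hospital or at home. Use one symptom list throughout: Aim 1 names gastrointestinal distress and itching, whereas Section 7b names constipation. In Section 7, make the questionnaire the source for the between-arm comparison of side effects, keep chart data as supporting, and state the analysis. Either add satisfaction to Section 7b with an analysis or drop it.

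The direct-questioning window is then 96 h in both arms, whatever the length of stay. The cost is a short wording change, earlier hand-out of a form that is already planned, and a few more short forms per inpatient, with some ward coordination at the four sites. It should be done before enrolment, because inpatient reports that were never asked for cannot be recovered later.

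### Is the enrolment of 120 wrong because 84 evaluable patients with 15% drop-out would give only 99 or 100?

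*Combined protocol and SAP*

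**What the plan says.** The size of the trial is described in two places in the combined protocol and SAP.

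- Section 7c (statistical plan) reports a non-inferiority power analysis on the VAS pain score: "The number was found to be 42 patients in each group, for a total n = 84". It then moves to enrolment: "To ensure we reach this number, each of the 4 sites will aim to enroll 30 patients, to account for drop out". No drop-out percentage is given there.
- Section 4a (Sample Size) gives the total: "There will be 60 patients in each group, for a total study population of n = 120". The Study Locations paragraph directly below adds a rate: "The sample size will enroll 120 (to account for 15% drop out rate) patients total, with approximately 30 patients enrolled at each site".

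Drop-out is the only reason offered for enrolling more than 84, and 15% is the only rate stated.

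**The concern.** The usual sample-size paragraph states a required number of evaluable patients and a drop-out rate, and the enrolment follows from the two. A reader who takes 84 and 15% from this plan and does that sum gets about 100. The stated figure is 120. The three numbers do not fit one derivation: 15% and 120 together imply 102 evaluable patients, while 84 and 120 together imply a 30% allowance. Section 4a attaches a rate to the 120, whereas section 7c reaches the same total from a per-site target.

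A mismatch like this can signal a real fault. The requirement might have changed without the enrolment being updated, the drop-out rate might be wrong, or more people might be randomised than the design can justify. The number of participants is something an ethics board and a statistical reader will want to trace, so the check is worth making.

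**Working it through.** **Inputs.** Evaluable patients required: 42 per group, 84 in total (section 7c). Drop-out rate: 15% (section 4a, Study Locations). Enrolment: 120, 60 per group (section 4a, Sample Size). Sites: 4, with a target of 30 each (section 7c).

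**Step 1: reproduce the plan's figure.** Four sites × 30 = 120, and 2 × 60 = 120. The total agrees with the site target and with the group sizes.

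**Step 2: try to reach 120 from 84 and 15%.**

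| Route | Calculation | Enrolment |
|---|---|---|
| Divide the total by (1 − d) | 84/0.85 = 98.8 | 99 |
| Divide per group, round up | 42/0.85 = 49.4, so 50 | 100 |
| Multiply the total by (1 + d) | 84 × 1.15 = 96.6 | 97 |
| Round the first route to four equal sites | 98.8/4 = 24.7, so 25 each | 100 |
| Apply 15% twice (no basis in the text) | 84/0.85² = 116.3; 84 × 1.15² = 111.1 | 117; 112 |

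None gives 120. The excess over the plain inflation is 120 − 99 = 21 or 120 − 100 = 20.

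**Step 3: work back from 120.** At 15% loss, 0.15 × 120 = 18 patients are lost and 102 remain, 51 per group. That is 102 − 84 = 18 above the requirement. To fall to 84, the trial must lose 120 − 84 = 36 patients, and 36/120 = 30%.

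**Step 4: ask what 99 or 100 would deliver.** Dividing by 0.85 makes the expected number of evaluable patients equal to the requirement, so a shortfall by chance is quite likely. Assume that each patient drops out independently with probability 0.15, so that the number evaluable among n enrolled is binomial(n, 0.85).

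| Enrolled | P(at least 84 evaluable in total) |
|---|---|
| 99 | 0.585 |
| 100 | 0.672 |
| 120 | above 0.9999 |

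The power analysis asks for 42 in each group, so the more relevant quantity is the probability that both groups reach 42. It is the square of the single-group probability:

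| Per group | P(one group has at least 42) | P(both groups have at least 42) |
|---|---|---|
| 50 | 0.668 | 0.446 |
| 54 | 0.947 | 0.897 |
| 55 | 0.970 | 0.942 |
| 60 | 0.999 | 0.998 |

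Section 7c sets out to make sure that the required number is reached. A plan with that aim and a 15% rate would choose something clearly above 50 per group. The 60 per group meets the aim with room to spare.

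**Step 5: effect on power.** The plan gives no alpha, power or standard deviation, and although it cites a minimal clinically important difference of 1.4 cm, it does not name that as the margin. Assume a margin of 1.4 cm and a true difference of 0. Under the normal approximation, 42 per group then implies these standard deviations, and 51 per group these powers:

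| One-sided alpha | Intended power | Implied SD (cm) | Power at 51 per group |
|---|---|---|---|
| 0.025 | 80% | 2.29 | 87% |
| 0.025 | 90% | 1.98 | 95% |
| 0.05 | 80% | 2.58 | 86% |
| 0.05 | 90% | 2.19 | 94% |

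In each case the surplus raises power by 4 to 7 percentage points over the intended level.

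**The case for a change.** The strongest case for a change is that the sample-size justification should be reproducible, and this one is not. Its only stated reason for exceeding 84 is drop-out, its only rate is 15%, and that rate supports 99 or 100. Calling 120 a round site target does not close the gap, because four equal sites of 25 would already provide 100 and section 7c again justifies the 30 per site by drop-out. Only the sponsor knows whether the surplus is a deliberate buffer, a convenient site target or a slip. One added sentence would settle it.

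The arithmetic in this argument stands: the numerical link from 15% to 120 is missing. Two parts of it do not hold. First, the parenthesis in section 4a says that the enrolment takes account of 15% drop-out; it does not say that 120 is 84 divided by 0.85. Read as an allowance, the statement is true. Second, section 7c does give a reason, namely to secure 84 evaluable patients, and a means, four sites of 30.

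The benchmark of 99 or 100 is also weaker than it looks. It is an expected-value minimum. A sentence saying that 100 would be enough would mislead, since the chance of reaching 42 in both groups would be below one half.

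**Conclusion.** The mismatch is real but needs no change. The plan meets every figure it states: 60 per group, four sites of 30, and more than 84 evaluable patients after 15% loss. The surplus of 20 or 21 patients over the plain inflation lies in the safe direction. It leaves about 102 evaluable at 15% loss and tolerates 30% loss overall before falling to 84. Anyone revising the text would keep 120, and no estimate, test or procedure would differ. The gain would be an explanatory sentence only.

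Two limits apply. The probabilities rest on independent drop-out at 15%, and clustering of losses by site would make them less favourable. More importantly, the reassurance covers only the step from 84 to 120. Whether 42 per group is itself adequate is a separate matter that cannot be checked without the alpha, power and standard deviation behind it.

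### Masking the outcome assessor cannot remove patient reporting bias from a self-scored 24-hour VAS, and the plan does not say who collects that score in hospital

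*Combined protocol and SAP*

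**What the plan says.** Section 7a names the primary outcome as "VAS pain score at 24 hours postop". The inpatient data list in section 4a has "Patient VAS scores every 6 hours after surgery". From discharge onward the plan says "Patients will record the following information after discharge up until 96 hours from their surgery"; the items are VAS, pain medication, opioid side effects and satisfaction. At the first postoperative visit, "Patients will record their VAS pain scores again at their". Aim 1 in section 2 takes the data "from inpatient medical records and through daily follow-up questionnaires after patients are discharged until 96 hours after surgery".

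On masking, section 4c opens with "Patients will be masked by performing the ISNB under sedation". It then says that blinding is incomplete, because the liposomal bupivacaine group has no neck puncture. It ends with "While the patient and surgeon cannot be blinded for this study, the outcome assessor will be masked to prevent bias in the data collection process".

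The only other mention of the masked assessor is under After Discharge in section 4a, beside the reminder calls: "The outcome assessor will be blinded to the treatment group".

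**The concern.** Section 4c makes three statements about the patient: masked, not completely blinded, and not able to be blinded. It then offers a masked third party as the measure against bias. For a self-scored scale the patient is the assessor, so masking someone else leaves the patient's own knowledge or expectation untouched. The same applies to side effects and satisfaction recorded by the patient.

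Section 7c sizes the trial for noninferiority on VAS. There, a reporting shift toward the new technique makes a false noninferiority conclusion more likely, and a shift toward the block makes a true one harder to reach. A reader who took the last sentence of 4c as covering the primary outcome would think this risk was handled.

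**Working it through.** **Step 1: who scores, who collects, who is masked**

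| Time | Who scores the VAS | Collector named? | Collector stated to be masked? |
|---|---|---|---|
| In hospital, including 24 h for inpatients | Patient (4a) | No; Aim 1 points to the medical record, and 4f calls VAS assessment routine | Only by the general sentence in 4c |
| Discharge to 96 h | Patient (4a) | Patient record, with possible staff reminder calls | Yes (After Discharge) |
| First postoperative visit | Patient (4a) | Patient record; study team calls if no visit falls in the window (4b) | Not stated separately |

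The explicit assessor masking sits after discharge. In the retrospective cohort (section 3), 16 of 37 and 2 of 21 patients, that is 18 of 58 (31%), left on the day after surgery, and mean stays were 46 and 57 hours. If practice is similar, most 24-hour scores will be taken in hospital, where no collector is named.

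**Step 2: what masking the collector can do**

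It can limit leading questions, selective prompting and errors in transcribing the record. It cannot change what the patient knows when marking the scale.

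**Step 3: the plan's own figure**

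Section 7c gives 42 per group and an MCID of 1.4 cm. It gives no SD, alpha or power, so 42 cannot be reproduced directly. Taking 1.4 cm as the margin and a true difference of zero, the implied SD is 1.4 / [(z for 1 − alpha + z for power) × √(2/42)]:

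- one-sided 0.025, 80% power: 1.4 / [(1.960 + 0.842) × 0.2182] = 2.29
- one-sided 0.025, 90% power: 1.98
- one-sided 0.05, 80% power: 2.58
- one-sided 0.05, 90% power: 2.19

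**Step 4: illustration of the stakes**

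Assumed: SD 2.3, one-sided alpha 0.025, margin 1.4 cm, and a constant reporting shift b. The number per arm is 60 × (1 − 0.15) = 51, from the enrolment and dropout in section 4a.

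SE = 2.3 × √(2/51) = 0.455.

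Shift toward liposomal bupivacaine, with a true deficit equal to the margin: false noninferiority rate = P(Z > 1.96 − b/SE).

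- b = 0: 2.5%
- b = 0.3: 9.7%
- b = 0.5: 1.96 − 1.098 = 0.862, giving 19.4%
- b = 0.7: 33.6%

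Shift toward the block, with no true difference: power = P(Z < (1.4 − b)/SE − 1.96).

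- b = 0: 3.074 − 1.96 = 1.114, giving 87%
- b = 0.5: 1.976 − 1.96 = 0.016, giving 51%

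Sensitivity at b = 0.5 toward liposomal bupivacaine, over SD 2.58 to 1.98: false noninferiority is about 14% to 21% with 42 per arm and about 18% to 28% with 60 per arm.

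**The case against.** Four stronger conclusions are tempting, and the documents support none of them.

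*That there is no protection at all.* Section 4c claims only to prevent bias in data collection. A masked staff member has a real, narrow use in reminder calls, in the call for patients without a visit in the window, and in record abstraction. Sedation adds some patient masking. This objection stands.

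*That the plan hides the problem.* It does not. Section 4c says masking is incomplete and gives the reason. Its three statements can even be read as graded: some masking, not complete, so not truly blinded. That softens the contradiction. It does not change the last sentence, which presents the assessor as the answer to unblinded patients.

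*That expectation will favour the new technique.* The direction cannot be read from the plan. The abstract calls the interscalene block the gold standard, and also cites better pain control with liposomal bupivacaine in knee and hip surgery. The retrospective cohort favours liposomal bupivacaine at 18–24 hours. What patients will be told about each arm is not in the material available.

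*That about 19% is this trial's error rate.* The shift, SD and alpha are assumptions, and 1.4 cm is given as an MCID, not stated as a margin. The tests in section 7c are rank-sum tests and a mixed model, with no noninferiority test or confidence limit. The figure only shows how sensitive such a comparison would be.

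A last objection is that concealing the neck site may achieve little, since only the block group has a preoperative procedure, and numbness or recall may reveal it. This is fair and limits the benefit. The puncture is nonetheless the only cue the plan itself names.

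**Conclusion.** The point holds in a limited form. The primary outcome and the patient-recorded secondary outcomes are scored by people whom section 4c says cannot be blinded. Assessor masking therefore addresses prompting and transcription bias but not patient reporting bias. The plan also leaves open who obtains the inpatient 24-hour VAS and whether that person is masked.

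No bias has been shown, and its size and direction are unknown. With every value in the calculation assumed except the 1.4 cm and the enrolment and dropout figures, a 0.5 cm shift moves false noninferiority from 2.5% to about 19%, or power from about 87% to 51%, depending on its direction. This is an inexpensive improvement to conduct and wording, not a flaw that invalidates the design.

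**What to change.** In section 4c:

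1. Apply the same small neck dressing to both groups once the patient is anaesthetised, and do not disclose allocation to the patient until the 96-hour form is complete. This covers the one unmasking cue the plan names without a sham injection.
2. State that the inpatient 24-hour VAS is either self-completed by the patient or recorded by existing staff who are not told the allocation.
3. Reconcile the three statements on patient blinding. Limit the assessor sentence to collection and transcription bias, and state that patient-reported outcomes are only partly masked.

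A question asking patients to guess their group is optional and should be reported descriptively only. Do not compare VAS by guess: the guess comes after randomisation and is shaped by the pain just felt, so the comparison would mix unmasking with real effect.

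Cost: a dressing per patient, some rewording, and the cooperation of ward staff at four sites in withholding allocation. No extra staff are needed. Masking will stay incomplete, because arm numbness or recall of the preoperative block may reveal the group.
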